***Exclusion Criteria***

1. Ongoing insulin therapy
2. Endoscopy within past 6 weeks
3. Use of anti-obesity drugs, or less than 3 months of discontinuation
4. Serum creatinine levels higher than 1.5 mg/dL
5. Hepatic enzyme elevation > 2x the upper limits of normal

6. Pregnant
7. Abnormal ECG
8. Prior bariatric surgery
9. Prior surgery on the alimentary tract
10. Gastroparesis
11. Inflammatory bowel disease
12. Currently using "blood thinners"
13. Pre-existing cardiovascular diseases
  - Heart attack in the past 3 months
  - Cardiac stenting
  - Heart valve disorders
14. Liver failure

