## 5. Screening and Enrollment

Obese subjects ( $\text{BMI} \geq 30 \text{ kg/m}^2$ ) with prediabetes or type 2 diabetes ( $n = 20$ ) will be recruited by solicitation flyers, recruitment emails using Research Match and LISTSERV that reaches all Vanderbilt employees, residents, and students, and Facebook advertisements. Subjects who do not qualify for bariatric surgery, or subjects who are awaiting insurance approval for a bariatric procedure at the Center of Surgical Weight Loss, One Hundred Oaks (OHO) at Vanderbilt University Medical Center will also be contacted via emails and telephone calls.

Subjects will undergo an initial screen by the study coordinator or research staff to assess eligibility and ability to comply with the study requirements. Prior to each study visit, subjects on oral anti-diabetic medications will be asked to discontinue these medications 4 days prior to their study visit. Diabetic subjects will be instructed to monitor their pre-prandial blood glucose during this time and to contact the study physician if their blood glucose levels are greater than 250 mg/dL for two consecutive readings. The study physician may instruct the subject to initiate short-term insulin therapy or resume their oral anti-diabetic medications; in either case the subject will be excluded from the study. Subjects will be instructed to maintain their usual diet and physical activity levels for 1 week prior to each study visit and to arrive fasted for every visit (only water after dinner).

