## Study visit 2 (within 2 weeks after the first visit):

- Subjects will undergo esophagogastroduodenoscopy (EGD) procedure for the delivery of BOTOX to the duodenal wall, to be performed by [name] at the Vanderbilt Gastrointestinal Endoscopy Suite (VGIES). We have been exempted from Investigational New Drug (IND) regulation for the proposed testing by the FDA (letter attached).
- Subjects will be monitored in the VGIES for 30 minutes and discharged with instructions for follow-up and contact information of the physicians' team (Drs. [name], [name]).

**Telemedicine visit** (1 week after SV2): Study team member will contact subject by telephone to assess if there have been any adverse events from the study procedures completed thus far.

**Study Visits 3-5** (1, 3, and 6 months after EGD): On every study visit, body weight, body composition via DEXA, food intake, and feeding behavior will be recorded and post-absorptive OGTT will be performed. Nutrient sensing test will be repeated at visit 3.

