## 11. Statistical Analyses

Sample Size: We hypothesize that Botox will reduce body weight, improve glucose tolerance, and augment lipid sensing during fasting and post-prandially, in Class I-III obese subjects. Our outcome measures for the effects of Botox are: body weight; area under the curve (AUC) for plasma levels of ghrelin, CCK, GIP, and GLP-1; and glucose AUC. Power calculation based on previous studies was performed using nQuery Advisor software. The number of subjects needed to detect a 15% decrease in body weight ( $n=16$ ), 10-15% decrease in plasma levels of gut peptides ( $n=14-16$ ), and a 10% decrease in glucose AUC ( $n=16$ ) was determined for an estimated 90% power (two-sided type I error rate = 0.05), with effect size of 0.25. We anticipate studying 20 subjects to account for attrition.

Statistical Analysis Plan: We will analyze pre- and post-intervention measurements at 1, 3, and 6 months using one-way repeated measures ANOVA for each outcome. Correlation between visits will be determined by the first-order autoregressive (AR1) rule which assumes that correlation among repeated measures decline exponentially with time. We will also determine the most optimal (1, 3, or 6 months) and inter time point differences for each outcome.

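### Eligibility does not clearly cover non-insulin injectable glucose-lowering drugs and requires no stable regimen before visit 1, so a recent drug change can pass for a Botox effect or hide a small one

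*Combined protocol and SAP*

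**What the plan says.** Two exclusion criteria in Section 4 concern drugs that affect glucose or weight: "Ongoing insulin therapy" and "Use of anti-obesity drugs, or less than 3 months of discontinuation". Anti-obesity drugs are not defined. The inclusion criteria ask for a diagnosis of type 2 diabetes or pre-diabetes and set no condition on treatment.

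Section 5 states that before each visit "subjects on oral anti-diabetic medications will be asked to discontinue these medications 4 days prior to their study visit". Diabetic subjects with two consecutive pre-meal readings above 250 mg/dL call the study physician. The next step reads "The study physician may instruct the subject to initiate short-term insulin therapy or resume their oral anti-diabetic medications", and either instruction removes the subject from the study. The only stability instruction concerns diet and exercise habits in the week before a visit. Recruitment includes "subjects who are awaiting insurance approval for a bariatric procedure".

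For the follow-up visits, Section 6 says "body weight, body composition via DEXA, food intake, and feeding behavior will be recorded", together with an OGTT. Medication is not on that list.

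Section 11 states: "We will analyze pre- and post-intervention measurements at 1, 3, and 6 months using one-way repeated measures ANOVA for each outcome". It adds: "Correlation between visits will be determined by the first-order autoregressive (AR1) rule". There is no comparison group and no step for concomitant medication.

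**The concern.** Each subject is his or her own control, so whatever moves weight or glucose between visit 1 and month 6 is counted as the Botox effect. Someone who started or titrated a glucose-lowering drug shortly before visit 1 may still be responding to it, and that looks like benefit. Someone who recently stopped may be regaining weight, and that hides benefit.

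The existing rules do not reach these cases:

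- The 4-day hold limits acute drug effects on the OGTT. It does nothing about slower changes in weight.
- The hold names oral drugs only. An injectable has no pre-visit instruction, so the interval since the last dose can differ between one subject's visits.
- Removal under Section 5 follows a physician's instruction during the hold. It does not detect a regimen change made weeks earlier.
- The hold obliges staff to ask about oral drugs, but nothing in the documents asks for start dates or dose changes. The visit forms are not among the documents.

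The plan already accepts the principle: it requires 3 months off anti-obesity drugs. People awaiting bariatric approval may plausibly have had recent treatment changes, although no rate is given. Long-stable users are not the problem, because a constant drug effect adds little to a within-subject change.

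**Working it through.** **The plan's own figure.** Section 11 gives n = 16 for 90% power, two-sided 0.05, effect size 0.25. Take a one-group repeated-measures ANOVA with 4 visits and read 0.25 as the variance of the visit means divided by σ²(1 − ρ). Then λ = 16 × 4 × 0.25 = 16, with 3 and 45 degrees of freedom. Power is 0.910, and 16 is the smallest n that reaches 90%. The correlation is not stated; reading 0.25 as Cohen's f gives the same n only at ρ = 0.75. Allowing 20% attrition, 16/0.8 = 20, the planned enrolment.

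**Shift in the mean.** If k of 16 completers each carry a drug-related change of X points after visit 1, the mean moves by kX/16. Both k and X are assumptions.

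- Weight, one subject: 5/16 = 0.31 and 10/16 = 0.63 points, or 2–4% of the planned 15%.
- Weight, two subjects: 0.63 to 1.25 points, or 4–8% of 15%.
- Glucose AUC, one injectable user with a 10–20% change: 10/16 = 0.63 and 20/16 = 1.25 points, or 6–13% of the planned 10%. The hold makes this less likely for oral drugs.

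**Effect on the planned test, weight.** I simulated the Section 11 analysis with 40,000 runs per setting: n = 16, visits at 0, 1, 3 and 6 months, F-test for visit with AR(1) errors fitted by REML, 3 and 45 df. Assumed: AR(1) by visit order (ρ 0.8, 0.9) or by month (ρ 0.9, 0.95); SD of the 0–6 month change 3 or 5 points; Botox and drug effects linear over 6 months. Ranges run over these settings.

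False-positive rate with no Botox effect (nominal 5%):

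- nobody affected: 4.9–5.1%
- one starter, 5 or 10 points: 4.8–5.3%
- two starters: 5.7–11.5%
- one starter plus one stopper, 10 points each: 0.8–3.1%

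A single starter shifts the mean but also widens the variance, so the test does not reject more often.

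Power when Botox works and one recent stopper regains weight:

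| True loss | SD | Nobody affected | 5-point regain | 10-point regain | Affected subject left out (n = 15) |
|---|---|---|---|---|---|
| 3 | 3 | 91.6–94.7% | 81.8–87.0% | 62.2–67.7% | 89.1–93.1% |
| 3 | 5 | 47.0–52.6% | 36.4–42.2% | 26.7–29.9% | 43.5–49.6% |
| 5 | 3 | 100% | not run | 99.7–99.9% | not run |
| 5 | 5 | 91.4–94.7% | not run | 78.7–83.7% | not run |

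With a true 15-point loss and two 10-point regains, power stays at 100%.

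**Effect on glucose AUC, simpler check.** A paired t-test with n = 16 has 90% power at a standardised change of 0.868, so a 10% fall implies an SD of change of 10/0.868 = 11.5 points. At that SD, two subjects with drug-related falls of 10% or 20% give 5.9% or 7.4% false positives. Two with rises of the same sizes lower power for a true 10% fall from 90% to 79% or 56%.

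**The case against.** The strongest reply is that the plan aims at a 15% loss, and Section 12 expects 10–15%. At 15 points nothing here changes the result, and failing to detect 3 points in a pilot does not defeat the stated aim. This stands as a limit on importance. The target, however, is carried over from mice on the stated assumption that humans respond alike, so a smaller human effect is a realistic outcome.

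Second, the sizes depend on assumed inputs. A 10-point regain after visit 1 is extreme, and staff might class a drug that powerful as anti-obesity and exclude it already. With a 3-point regain, power for a 3-point loss falls only from 95% to about 92% (SD 3) or from 51% to about 45% (SD 5). Using instead the SD that gives 90% power for a 15% loss, 15/0.868 = 17.3, a paired t-test loses only 90% to 87% from one 10-point regain, and two 10-point starters raise false positives only to 5.4%. An SD of 17.3 may be too large, but the dependence on assumptions is real. That an injectable might be caught by the anti-obesity rule also confirms that the wording leaves it to staff judgement.

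Third, false attribution to Botox needs at least two recent starters in the same direction before the test is affected, and recruitment by flyer and staff email is not enriched for them. This is correct.

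Fourth, changes during follow-up are as plausible a source of drift, and eligibility cannot prevent them. This also stands: the remedy is partial, and the basic limitation is the uncontrolled design.

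**Conclusion.** The concern holds, at modest weight and with medium confidence. Followed exactly as written, the protocol can enrol a subject whose glucose-lowering treatment has just changed, gives no rule for non-insulin injectables, and analyses the result without a control group or a medication step.

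The likely bias in mean weight is small: 0.31 to 1.25 points for one or two affected subjects under the assumed 5 to 10 points each. It cannot produce the planned 15% loss. One starter does not inflate the false-positive rate. The clearest consequence is missing a true loss of about 3 points, or about 5 points when the SD of change is 5. All these sizes rest on assumed drug effects, numbers of affected subjects, SDs and correlations; the documents supply none of them. The concern is confined to people who recently started, titrated or stopped a drug.

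**What to change.** 1. In Section 4, require every glucose-lowering drug, oral or non-insulin injectable, to be at a stable dose for at least 3 months before visit 1, and any such drug that was stopped to have been stopped at least 3 months before. This reuses the plan's own window. State that a drug taken for weight loss stays excluded under the anti-obesity rule.
2. In Section 5, have permitted injectables continue at the same dose and with the same timing relative to visits 1 and 3–5.
3. In Section 6, record drug, dose, start date and changes at each visit.
4. In Section 11, pre-specify a sensitivity analysis without subjects whose regimen changed in the 3 months before visit 1. These would be subjects enrolled before the amendment and protocol deviations.
5. Report changes during follow-up descriptively. Do not exclude subjects for them, because they occur after treatment.

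Items 1 and 2 are the core; the others support them. The cost is a short amendment, one form item, one extra analysis and perhaps slightly slower recruitment. The sample size stays at 16 evaluable and 20 enrolled. In the simulation with a true 3-point loss, leaving out one of 16 subjects costs about 1.5 to 3.5 points of power compared with 16 unaffected subjects. A 3-month window reduces drug-related drift but may not remove all of it.

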**Strabismus:**

Strabismus patients receiving higher doses of BOTOX reported vertical deviation. About 17% of 2058 adults that received a total of 3650 injections for treatment of horizontal strabismus reported vertical deviation. Ptosis was reported in 1%, 16%, and 38% after injections in inferior rectus, horizontal rectus, and superior rectus, respectively. Retro bulbar hemorrhage was reported in 0.3% cases.

In general, local muscle weakness appears to be the most commonly reported and expected event following BOTOX injection in muscles. However, weakness of adjacent muscle tissues, and rarely remote tissues occurring as a result of “spread of toxin effect” have been reported in adult and pediatric patients as well. Events typically observed after any injection procedure including localized pain, inflammation, tenderness, bruising, erythema, and needle-related pain or anxiety have been reported in some clinical trials.

We will recruit obese subjects with pre-diabetes or T2D for the proposed clinical study for 5 visits. After informed written consent is obtained, subjects will be admitted to the Clinical Research Center (CRC), and will undergo upper endoscopic injection of Botox into the duodenal wall. We anticipate that injections of Botox into the duodenal wall will result in significant weight loss and improvements in glucose tolerance and duodenal nutrient sensitivity. Subjects will be studied over a period of 6 months. Subjects will be asked to complete 5 study visits: On the first visit, each subject will undergo an oral glucose tolerance test (OGTT). At visit 2, subjects will undergo an esophagogastroduodenoscopy (EGD) procedure for the delivery of BtX-A to the duodenal wall. Visits 3-5 will be made 1, 3, and 6 months after EGD (Figure 1). On every study visit, body weight and body composition will be recorded and oral glucose tolerance test (OGTT) be performed. Nutrient sensing test will be performed at visits 1 and 3.

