### **(d) Data Safety Monitoring Plan (DSMP).**

- Our DSMP will focus on performance, safety, and care of participants. [name], Columbia University, and [name], Washington University St. Louis, will serve as the Data Safety Monitoring Board (DMSB) for this study.
- This is a pilot study. The DSMB will meet with the PIs at least 3 times. We are planning to initially enroll 3 patients and have the DSMB look at the efficacy and safety data. This will involve an initial meeting to ratify the DSMB, a meeting after the first patient undergoes EGD, and after 3 patients complete enrollment. The next meetings will be at the end of the first and second years, respectively. Progress reports will indicate patient recruitment status, adverse event occurrence, and summary of data collected. The DMSB will assess safety data including development of local or peripheral muscular weakness, bleeding, inflammation, hospitalizations, and other serious adverse events. Based on safety reports, the DMSB will advise and consent modification or termination of the study protocol or the study if it deems such actions to be warranted. Each meeting will be virtual, via zoom. We will send minutes to DSMB members for review and approval after each meeting.
- Participating subjects will be monitored by the physician and nursing staff of the VGIES PACU after recovering from anesthesia for EGD procedure and evaluated by physician prior to discharge.
- The research coordinator will be required to be present to record any AEs and report to the PI or co-investigators promptly of such events.

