## 10. Study Withdrawal/Discontinuation

Subjects will be informed that they can discontinue or withhold participation at any time for any reason. Subjects will be compensated for their time and participation.

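### As written, the glucose-rescue exclusion also removes subjects who have already been injected, ending their planned weight, DEXA, OGTT and safety visits

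*Combined protocol and SAP*

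**What the plan says.** Section 5 (Screening and Enrollment) sets the washout: "Prior to each study visit, subjects on oral anti-diabetic medications will be asked to discontinue these medications 4 days prior to their study visit". It continues: "Diabetic subjects will be instructed to monitor their pre-prandial blood glucose during this time". Two consecutive readings above 250 mg/dL require a call to the study physician. Then: "The study physician may instruct the subject to initiate short-term insulin therapy or resume their oral anti-diabetic medications". The consequence of both kinds of rescue is the same: "in either case the subject will be excluded from the study".

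Injection is at visit 2. The study overview at the end of section 3.2 adds: "Visits 3-5 will be made 1, 3, and 6 months after EGD". Section 6 sets what those later visits collect: "On every study visit, body weight, body composition via DEXA, food intake, and feeding behavior will be recorded", together with an OGTT.

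Section 10 (Study Withdrawal/Discontinuation) deals only with the subject's own choice: "Subjects will be informed that they can discontinue or withhold participation at any time for any reason". Section 11 gives no rule for rescue, missing data or analysis set. The safety monitoring plan in section 9 says: "The DMSB will assess safety data including development of local or peripheral muscular weakness, bleeding, inflammation, hospitalizations, and other serious adverse events". High glucose is not named there.

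**The concern.** The washout and the glucose rule are tied to each visit, and three of the five visits come after the injection. The stated consequence of rescue is removal from the study, not omission of one OGTT. No section keeps an injected subject in follow-up after such a removal, and none asks for a count of rescues.

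Two things are at stake. The first is follow-up. Section 1 says that this use of the drug is unexplored, and there is no control arm. A subject whose glucose rises after injection is one whose later weight, DEXA, OGTT and safety data are especially wanted. Weight (Aim 1) is lost too, although rescue is no reason to stop weighing. The second is the glucose result. Removal acts on high values only, and glucose tolerance is Aim 2, so the retained subjects may not represent everyone injected.

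**Working it through.** **1. The plan's own sample size.** Section 11 gives n=16 for a 10% fall in glucose AUC (90% power, two-sided 0.05, effect size 0.25) and plans 20. Reading the effect size as Var(means)/(SD²(1−ρ)) with four time points, the noncentrality is n × 4 × 0.25 = 16 at n=16, with 3 and 3(n−1) degrees of freedom. Power is 0.910, so 16 reproduces under this reading. The allowance is 20 − 16 = 4 subjects for all causes of loss. On the same formula, power is 0.888 at 15, 0.861 at 14 and 0.790 at 12.

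**2. Assumptions.** The documents give no rescue rate, glucose SD, between-visit correlation, share diabetic or spread of response. All of the following are assumed:
- 20 injected subjects; AUC level SD 1; between-visit correlation 0.5 or 0.7.
- Pre-visit glucose = 0.8 × AUC level + noise. The cut-off is set so that 2, 5, 10 or 15% of monitored subjects exceed it per visit if untreated.
- The rule is applied before visits 1 and 2 (failures are never injected), then cumulatively before visits 3-5.
- Share diabetic 1 or 0.5; share of triggers leading to rescue 1 or 0.5.
- Response uniform, or varying between subjects with SD 0.6.

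**3. Month-6 mean change in retained subjects when the true worsening is +0.40 SD.** Understatement = (0.40 − retained mean)/0.40.

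| Setting | corr. 0.5, 5% | corr. 0.5, 10% | corr. 0.7, 5% | corr. 0.7, 10% | Understated |
|---|---|---|---|---|---|
| Uniform; all diabetic, all rescued | 0.375 | 0.362 | 0.385 | 0.377 | about 4-9% |
| Varying; half diabetic, half rescued | 0.364 | 0.355 | 0.367 | 0.358 | about 8-11% (12% in a repeat run) |
| Varying; half diabetic, all rescued | 0.339 | 0.329 | 0.349 | 0.339 | 13-18% |
| Varying; all diabetic, all rescued | 0.255 | 0.200 | 0.277 | 0.226 | 31-50% |

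For example, (0.40 − 0.200)/0.40 = 50% and (0.40 − 0.362)/0.40 = 9.5%.

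**4. Other true effects.** A uniformly inert drug reads within 0.004 of zero. A uniform benefit of −0.40 reads −0.38 to −0.39. With zero mean effect but response SD 0.6, the retained mean is −0.04 to −0.14 at 2-15% per visit (−0.02 to −0.05 if half are diabetic). If the effect is present only at month 1, month 6 is unbiased and 19-31% of a month-1 worsening is hidden (varying response, all diabetic and rescued).

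**5. Follow-up lost under an inert drug.** At 2/5/10/15% per visit, all diabetic and all rescued, about 1/2/3.5/5 of 20 subjects and 2/4/7.5/10.5 of 60 post-injection visits are lost. With half diabetic and half rescued, 0.3/0.6/1.1/1.5 subjects are lost. The chance that fewer than 16 remain, with no other dropout, runs from under 1% to 64% in the first case and is at most 2% in the second.

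**6. A second model, in mg/dL.** Here the trigger is the outcome itself (washout mean 150-190, SD 35-45, AR(1) correlation 0.6-0.8). With no drug effect, 0.4-16.7% of injected subjects are removed and completers' mean change stays within 0.1 mg/dL of zero. With a uniform worsening of 15 mg/dL, 1.6-28.2% are removed and completers show 14.78 down to 11.76. That understates the truth by (15 − 14.78)/15 = 1% to (15 − 11.76)/15 = 22%. The direction agrees with step 3; the size depends on the model.

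**The case against.** **It may be an entry rule.** The sentence sits under a screening heading, follows the eligibility screen and speaks of exclusion, the term used for the entry criteria in section 4, where ongoing insulin is the first item. Leaving the study has its own section. This is a fair reading of intent, and it stands as a caution. But the same paragraph governs conduct before each visit, and nothing confines its consequence to entry.

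**The number affected may be small.** This stands. Prediabetic subjects are eligible but are not told to monitor. Two consecutive readings are needed, rescue is discretionary, and anyone rescued before visits 1 or 2 is never injected.

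**Rescues could surface elsewhere.** This stands in part. The monitoring board's list is introduced as non-exhaustive, its progress reports cover adverse events and recruitment, section 9 grades events needing medical attention, and there are early telephone calls and a 24/7 line. None of these requires a rescue count or replaces visits 3-5.

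**Stronger readings.** A reader might infer that the rule manufactures a glucose benefit. It does not for a uniformly inert drug. In the mg/dL model completers lie 0.1 to 6.4 mg/dL below all injected subjects, but that is because the all-injected mean drifts up by regression to the mean after the entry filter. A reader might also infer that the rule mainly conceals harm, or hides up to half of it. That needs varying response, every subject diabetic and every trigger rescued; the documents support none of these.

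**Conclusion.** The point holds as a gap in the wording with a real consequence for follow-up. Followed literally, the rule ends visits 3-5 for an injected subject rescued for high glucose. This does not depend on the simulations.

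The effect on the glucose result is conditional and of unknown size. Under the main model it is nil for a uniformly inert drug and a slight understatement of a uniform benefit. A 0.40 SD worsening is understated by about 4-9% if response is uniform (all diabetic, all rescued). With response SD 0.6 it is about 8-12% at half diabetic and half rescued, and 31-50% only in the extreme case. These figures assume 5-10% over the cut-off per visit. Whether the four-subject allowance would be used up cannot be judged without a rescue rate. The point should be fixed; confidence is medium because the intent is uncertain and the rates are assumed.

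**What to change.** - State that exclusion from the study applies only to subjects who meet the rule before the visit 2 injection.
- After injection, allow rescue exactly as now, but keep the subject in visits 3-5 for weight, DEXA and adverse events. Flag or omit only the affected OGTT.
- Analyse weight in all injected subjects.
- Report the number rescued at each visit beside the glucose result and to the monitoring board.
- State that the glucose AUC analysis in unrescued visits still drops high-glucose visits and must be read with the rescue count.

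The cost is protocol wording and one count per visit, with no added subjects or procedures.

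The sure gain is follow-up and visibility. Recovery of the glucose signal is partial: in the extreme case (varying response, all diabetic, all rescued) the month-6 mean in unrescued visits is about 0.28-0.33 against 0.40, so about 18-31% is still hidden. Detection is then 16-29%, against 10-20% under the present rule and 31-41% for 20 subjects with no exclusion at all (SD of change √(2(1−ρ) + 0.6²) = 1.166 or 0.980).

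A worst-rank glucose analysis could be added for sensitivity only. Because entry already removes high glucose, regression to the mean gives false worsening under an inert drug in 3-11% of trials at 2-15% per visit (nominal 2.5%). Power for a uniform benefit of 0.40 SD at 5-10% per visit falls to 22-46%, against 34-55% in retained subjects.

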#### **4. Inclusion/Exclusion Criteria**

***Inclusion Criteria***

1. Age = 18-65
2. BMI  $\geq 30 \text{ kg/m}^2$
3. Having established diagnosis of Type 2 diabetes or pre-diabetes

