## 8. Protection against risks

### 8.1. Recruitment and Informed Consent

- Subjects will be recruited via solicitation flyers, Research Match, LISTSERV, advertisements, and Facebook posts listing study objectives and design, inclusion criteria, remuneration, and contact information.
- Recruitment email will be sent using Vanderbilt’s “Research Notification” list that reaches all Vanderbilt employees and can therefore target a large population.
- In addition, census lists from the Vanderbilt Center for Surgical Weight Loss will be screened for eligible candidates, based on inclusion/exclusion criteria. Subjects who do not qualify for bariatric surgery, or subjects who are awaiting insurance approval for a bariatric procedure will be contacted via emails and telephone calls.
- Interested subjects will attend a pre-study seminar session entailing the study’s purpose, procedures, and potential risks. If subjects are still interested they will be directed to contact the recruiter for more information and additional screening. During the screening the recruiter will further review inclusion and exclusion criteria and explain the study procedures, duration of the study, benefits of participation, and potential risks, and answer any remaining questions.
- If the subject indicates interest, a copy of the informed consent will be provided (by hand, mail, or email); time will be allowed for the subject to read through the form and ask additional questions or express concerns.
- Subjects will sign the consent at the time of their screening visit to the Vanderbilt CRC. Signed consent forms will be uploaded to a secure password-protected REDCap® (Research Electronic Data Capture) database.

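### Weight change is read against a single pre-injection baseline with no control, yet entry requires neither a stable weight nor absence of a weight-loss programme, so pre-existing weight change can be counted as a Botox effect

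*Combined protocol and SAP*

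**What the plan says.** **Entry.** Section 4 has three inclusion criteria: age 18-65, BMI of at least 30 kg/m², and "Having established diagnosis of Type 2 diabetes or pre-diabetes". Of the 14 exclusions, two concern weight treatment: "Use of anti-obesity drugs, or less than 3 months of discontinuation" and "Prior bariatric surgery". None concerns recent weight change or a diet, exercise or behavioural programme.

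**Lifestyle.** Section 5 gives the one rule: "Subjects will be instructed to maintain their usual diet and physical activity levels for 1 week prior to each study visit". Usual diet is not defined.

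**Recruitment.** Flyers, e-mail lists and social media are used. Section 5 also names "subjects who are awaiting insurance approval for a bariatric procedure" and people who do not qualify for such surgery. Section 8.1 adds that "census lists from the Vanderbilt Center for Surgical Weight Loss will be screened for eligible candidates, based on inclusion/exclusion criteria".

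**Measurement.** Under Section 6, weight is measured at visit 1, the injection follows within 2 weeks, and weight is measured again 1, 3 and 6 months after it. A feeding-behaviour questionnaire is handed out at visit 1. Food intake and feeding behaviour are recorded at visits 3-5.

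**Analysis.** Section 11: "We will analyze pre- and post-intervention measurements at 1, 3, and 6 months using one-way repeated measures ANOVA for each outcome". There is one group, no covariate and no use of weights from before visit 1.

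**The concern.** In a single-group design, the change from baseline estimates the drug effect plus whatever would have happened anyway. With no control arm to subtract the second part, the plan relies on it being about zero. For body weight that is normally supported by requiring a stable weight at entry. Nothing here requires or checks it: the interval between baseline and injection is at most 2 weeks, and no earlier weights are collected.

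The sponsor has closed one such route, recent anti-obesity drugs, and left the non-drug equivalent open. A subject on a weight-loss diet at entry satisfies the one-week rule by continuing it.

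Two aims are exposed. Aim 1 is weight itself. For Aim 2, Section 12 acknowledges that sustained improvement in glucose tolerance may depend on weight loss, so background loss would probably move glucose AUC in the same direction.

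**Working it through.** **1. The plan's own figure.** Section 11 gives n = 16 for body weight at 90% power and two-sided 0.05, with an effect size of 0.25. In a one-way repeated-measures ANOVA with 4 time points, read 0.25 as the variance of the means over the within-subject error variance. The noncentrality is then 16 × 4 × 0.25 = 16 on 3 and 45 degrees of freedom, and power is 0.910. With n = 15 it is 0.888, so 16 is reproduced on this reading. 16/0.80 = 20 matches the enrolment target. The calculation concerns random error only and allows nothing for background change.

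**2. Coverage of the lifestyle rule after injection.** One week before each of visits 3, 4 and 5 is 3 of about 26 weeks: 3/26 = 11.5%.

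**3. Illustrative drift.** Assumptions, none from the documents: baseline 110 kg; affected subjects lose 0.25-0.5 kg/week without interruption; 4 of 20 affected; the others unchanged on average.

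- Per affected subject: 0.25 × 26 = 6.5 kg and 0.5 × 26 = 13 kg. Divided by 110 kg, this is 5.9% and 11.8%.
- Group mean: 5.9% × 4/20 = 1.2 points and 11.8% × 4/20 = 2.4 points.

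**4. Chance of a significant result with no drug effect.** This uses a paired baseline-to-6-month t-test, two-sided 0.05, as a simplification of the planned ANOVA. With share p losing g% and an assumed residual SD of 4%, the mean is pg and the SD is √(16 + p(1 − p)g²).

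| Scenario (assumed) | Mean loss | SD of change | n = 16 | n = 20 |
|---|---|---|---|---|
| p = 0.20, g = 5.9% | 1.2% | 4.6% | 16% | 19% |
| p = 0.20, g = 11.8% | 2.4% | 6.2% | 30% | 37% |
| p = 0.25, g = 5% | 1.25% | 4.5% | 18% | 21% |
| p = 0.50, g = 10% | 5.0% | 6.4% | 83% | 91% |

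The nominal rate is 5%. The rate rises from n = 16 to n = 20 in every row, so a larger sample does not cure the problem.

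**5. How tight a criterion must be.** A limit of L% over 3 months (13 weeks) permits 2L% over 26 weeks if the trend continues. For L = 5 at 110 kg: 5.5 kg/13 weeks = 0.42 kg/week, and 0.42 × 26 ≈ 11 kg, or 10%. A 5% limit would thus admit most of the 0.25-0.5 kg/week range and allow a loss equal to the low end of the 10-15% anticipated in Section 12.

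**The case against.** The strongest reply is that nothing shows any recruit to be losing weight. Not qualifying for surgery, or awaiting insurance approval, does not imply an active diet. People regaining weight after a diet, or after stopping a drug more than 3 months earlier, can also enter, and they would bias against Botox. This stands: the route is open, but its direction is not established. A reader might infer that the bias must favour the drug; the documents do not support that.

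Second, 26 weeks of steady loss fits poorly with Section 1, which describes lifestyle interventions as modest in effect and seldom sustained. The assumed group shift of 1.2-2.4 points is also small beside the 15% decrease in Section 11. Both points stand. A reader might infer that background loss could imitate the whole anticipated effect. Only an individual losing faster than about 0.42 kg/week reaches 10% in 26 weeks, and the illustrated group mean stays far below it. What drift can do is produce or enlarge a nonzero change.

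Third, it is tempting to say that the bias could never be untangled later. That is too strong: the visit 1 questionnaire and the food-intake and feeding-behaviour records at visits 3-5 could help to identify dieters. They are not in the planned analysis, however, and give no pre-entry trend.

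Finally, this is a pilot, and the root cause is the absence of a control group. That is true, but Section 11 still claims 90% power for weight, and an entry rule is a cheap partial protection.

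**Conclusion.** The concern holds as an open route to bias, not a demonstrated one. Sections 4 and 5 do not secure a steady weight at entry, and Section 11 attributes all change after the injection visit to the intervention. Pre-existing weight change can therefore be counted as a Botox effect on weight and, through weight, on glucose AUC.

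The size rests wholly on assumptions: 110 kg, 0.25-0.5 kg/week for 26 weeks and 4 of 20 subjects affected give a 1.2-2.4 point shift in the 6-month mean. With an assumed residual SD of 4%, the chance of a false finding in the simplified test is about 16-37% across n = 16 and n = 20. Fewer or slower losers, or an admixture of regainers, would reduce or reverse it. The change should be made because it is cheap and protects the lead aim.

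**What to change.** 1. **Section 4.** Add a weight-stability criterion over the 3 months before visit 1, matching the existing drug window, based on chart or self-reported weights. Set the limit tighter than 5% and state the 6-month drift that it would still permit (twice the 3-month limit if the trend continues). Require no enrolment in a structured weight-loss programme at entry.
2. **Sections 6 and 11.** Record the pre-entry weights and report the pre-entry trend beside the change after injection.
3. **During follow-up.** Record any weight-loss programme started on study. Give the weight result with and without those subjects as a sensitivity analysis only, since starting a programme may itself follow from response or non-response.
4. **Do not extend the usual-diet instruction through to visit 5.** It could suppress a satiety-driven change in intake, which Sections 1 and 2 propose as part of the mechanism and Section 6 sets out to record.

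**Cost.** Protocol wording and existing or self-reported weights; no new visit, test or change in sample size. Some weight-loss-clinic candidates would be lost or delayed until stable. The criterion does not remove loss that begins after enrolment and does not replace a concurrent control group; the report should say so.
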